6.3.3 Quality of Life

The analyses of the quality of life will be realized thanks to following endpoints, assessed every month over the AXI treatment:

FKSI-19 score

The FKSI-19 score will result of completed answers from FKSI-19 questionnaire (Functional Assessment of Cancer Therapy Kidney Symptom Index-19) (version 4) (presented in appendix **Error! Reference source not found.**). This scale assesses symptoms of importance to patients with advanced kidney cancer, with 19 items:

- 12-item subscale about Disease Related Symptoms Physical (DRS-P);
- 1-item subscale about Disease Related Symptoms Emotional (DRS-E);
- 3-item subscale about Treatment Side Effects (TSE);
- 3-item subscale about Function/ Well-Being (FWB).

This score will be assessed for each subscale and overall, as sum of item scores. Scoring guidelines are presented in appendix **Error! Reference source not found.**

Mental Health (MH) score of SF-36

The score of Mental Health (MH) domain of the Short Form (36) Health Survey (SF-36) will be defined as the sum of scores of items, divided by 5 (items presented in appendix 12.3). Scoring guidelines are presented in appendix **Error! Reference source not found.**

Role-Emotional (RE) score of SF-36

The score of Role-Emotional (RE) domain of SF-36 questionnaire (presented in appendix 12.3) will be defined as the sum of scores of items concerned, divided by 3 (items presented in appendix 12.3). Scoring guidelines are presented in appendix **Error! Reference source not found.**

Change in scores from baseline

This endpoint will be defined for the three scores mentioned above, as the difference between QoL score at visit every month over AXI treatment and the score at AXI initiation.

6.4 COVARIATES

In case of multivariate analyses, baseline characteristics will possibly be used as covariates.

Possible, but not exclusive, baseline covariates related to SU initiation will be limited because of a retrospective part of the data collection, with:

- Age and sex
- ECOG (0, 1, 2, 3, 4), Karnofsky performance status
- MSKCC risk factors (first line) (Good, Intermediate, Poor)
- Heng risk factors (Favorable, Intermediate, Poor)
- Medical history of hypertension (Yes, No)
- Delay from diagnosis (< 1 year from diagnosis to first metastasis detection/ ≥ 1 year)
- Nephrectomy (Yes, No)
- Number of metastasic sites.

The covariates identified previously will be also explored if the baseline is the AXI initiation. In this case, other covariates will be:

- The response to SU treatment in 1st line
- Duration of SU treatment, PFS
- Previous treatments for primary tumor (surgery, radiotherapy, other);
- Additional anti-tumor treatments

7 HANDLING OF MISSING VALUES

The majority of data will be collected with a website (except for FKSI-19 and SF-36 questionnaires). In this website, the input of certain data will be obligatory, limiting the number of missing values, particularly for endpoints.

Regarding the descriptive analyses of each variable, it will be based on the available data ("observed-case analysis"), considering missing data as non-informative. The number of missing data will be documented for each analysis.

The analysis of the primary endpoint is a survival analysis which is known to efficiently handle missing data: all patients are included in the analysis and missing data are called right-censored data.

For continuous endpoints (QoL endpoints), a mixed model for repeated measures (MMRM) will be used to analyse longitudinal data. Missing data will not be imputed. However, this analysis will be performed on all patients having a baseline value and at least one post-baseline value. The model will be valid under the assumption of data missing at random (MAR).

8 STATISTICAL METHODOLOGY AND STATISTICAL ANALYSES

8.1 STATISTICAL METHODS

Statistical analysis will be performed with SAS software (version 9.4 or higher, SAS Institute, North Carolina USA).

8.1.1 Descriptive Methods

Descriptive analysis of qualitative and ordinal variables will comprise the number and percentage of each category. Percentages will be calculated on the number of all available data, excluding missing data.

Descriptive analysis of quantitative variables will present the mean, the standard deviation (SD) as well as the median, quartile 1, quartile 3, min and max values.

The 95% confidence intervals will be presented for main endpoints. The 'exact' Clopper-Pearson confidence interval will be provided to assess 2-sided 95% confidence interval for main binomial proportions (e.g. ORR rate).

The number of missing values will be reported in the results table for each variable.

8.1.2 Survival Analysis Methods

The survival functions (for PFS, TTF, TSF, OS) will be estimated with the Kaplan-Meier method. The survival function S(t) is the probability that the event (treatment discontinuation, death or progression) does not occur before a specified time.

This method will be applied to derive, survival curves, median event time and a 95% confidence interval for the median survival time (time at which half the analyzed patients have presented the event). Survival curves will give an idea of whether or not the groups are proportional (i.e. the survival functions are approximately parallel). For OS, the share of patients alive at 24 months will also be measured.

The log-rank test of equality across strata will be used to compare survival curves for categorical variables (sub-groups of interest). For continuous variables, a univariate Cox proportional hazard regression will be used.

For analyses of prognostic factors of survival time, multivariate Cox proportional hazard regressions will be performed.

8.1.3 Strategy of Variable Selection in a Cox Model for PFS Analysis

The strategy of selection of variables in multivariate models will consist in: *Step 1: Selection of initial factor*

In a first step, the association between the PFS and each potential factor will be analyzed using

- A Log-Rank test (PROC LIFETEST under SAS 9.4) for categorical factors. Kaplan-Meier curves will also be presented in order to give an idea of whether or not the corresponding groups are proportional (i.e. the survival functions are approximately parallel)
- a univariate Cox proportional hazard regression (PROC PHREG under SAS 9.4) for continuous factors

Only significant factors at the 25% threshold will be retained for the initial model.

The possible correlations between the factors selected will be investigated. This will be done using

- A Chi-2 or Fisher-exact tests (if at least one number is less than 5) for 2 categorical factors
- An Analysis of Covariance (ANCOVA) for 2 continuous factors or for a categorical and a continuous factor.

Since two highly correlated factors (p-value <5%) cannot be present in the same model, a clinical arbitration can be requested if necessary.

Step 2: Selection of final factors

For this step, a Cox model will be run (PROC PHREG under SAS 9.4). In a first step, all the factors retained at the end of step 1 will be introduced to the model. PFIZER CONFIDENTIAL

Then a backward elimination procedure will be used in order to retain only independently significant factors at the 5% threshold.

Step 3: Investigate possible interactions between final factors

When the final model has been reached, interactions will be introduced to verify their non-significance. The existence of an interaction between two variables means that the effect of one variable is different depending on the other variable; it will have to be taken into account in the interpretation.

8.1.4 Analysis of Longitudinal Data

Mixed models with Repeated Measures (MMRM) will be used to analyze longitudinal data (QoL over the AXI treatment). These models will allow to answer questions as "Are there significant changes in the endpoint from baseline?" or "Do any groups differ at any time point regarding the endpoint?".

In order to explore possible variations in time and the possible differences according to the best response observed under Axitinib treatment, each QoL score/subscore will be analyzed using a mixed model for repeated measures (MMRM) (using the SAS MIXED procedure) with:

- The absolute difference in score/sub score as endpoint (MODEL statement of the MIXED procedure)
- The time, the best response observed under Axitinib treatment, and the interaction between these 2 covariates as fixed effects (MODEL statement of the MIXED procedure). All these variables will be considered as categorical ones. Please refer to appendix **Error! Reference source not found.** of this document for the definition of monthly time windows
- The Baseline value and baseline-x-time interaction as covariates. This variable will be considered as continuous one
- A time repeated effect (REPEATED statement of the MIXED procedure) within each subject (SUBJECT = USUBJID as option of the REPEATED statement). This will permit to take into account the fact that for each subject, several measures are performed over time. The type of variance covariance matrix will be the unstructured one in a first time (TYPE = UN as option of the REPEATED statement). If the model with the unstructured covariance matrix fails to converge, other covariance structures including Toeplitz, compound symmetry, and spatial power will be considered. The covariance structure converging to the best fit, as determined by a minimal Akaike's information criterion (AIC), will be used as the primary analysis. The Kenward-Roger approximation will be used to estimate denominator degrees of freedom.

In order to explore the validity of the model (and more precisely the assumption regarding independence, normality and constant variance of residuals), the following graphs will be provided:

- Q-Q plot of the residuals
- Distribution of residuals with its corresponding Normal density estimate
- Scatterplot of Residuals vs. Predicted values

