Because of the inclusion criteria (Patients being treated with SU in 1st line according to the European approved therapeutic indication and/or being treated with AXI in 2nd line according to the European approved therapeutic indication (except post cytokines)), the medication is prescribed within the regular practice of the physician. Because of the non-interventional nature of the study, there will be no specific requirements with regards to the treatment process. The physician will determine dosage and duration of the treatment, guided by the SmPC and according to his assessment of the individual therapeutic needs of the patient.

The QoL questionnaire will be completed at baseline and then every month for patients receiving AXI. QoL will also be measured at the discontinuation of AXI treatment. Patients will complete the QoL questionnaire at their homes once per month and return it using pre-stamped envelopes. If not done before, the questionnaire will be completed at the site preferentially prior to the follow-up visit(s).

If QoL objective is locally non-compliant with a non-interventional study design, patients will be exempted from performing the questionnaires.

Figure 2 : visit scheme

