The OS will be defined as the time from date of first SU dose to the date of death of any cause. For patients not experiencing the event, their survival times will be censored at the last date they are known to be alive

Variable name	Definition
OS status	Patient will not be censored for the OS analysis (OS status = 1) in the following cases:
	1) Axitinib discontinued due to Death (cf. CRF page 35)
	2) Death reported in Long term Follow-up (cf. CRF page 36)
	 Death reported on the Study Discontinuation form (cf. CRF page 37)
	In all other cases, patient will be censored for the OS analysis (OS status $= 0$).

OS status and OS time will be calculated as detailed below:

Variable name	Definition					
OS time	The overall survival time will be calculated in months as:					
(months)	 (Date of death reported at time of Axitinib discontinuation - Start date of Sunitinib + 1) / 30.44, if case n°1 described above is reported 					
	 (Date of death reported in Long term Follow-up - Start date of Sunitinib + 1) / 30.44, if case n°2 described above is reported 					
	 (Date of death reported on the Study Discontinuation form - Start date of Sunitinib + 1) / 30.44, if case n°3 described above is reported 					
	Else, the overall survival time will be censored as follows:					
	 (Maximum of {All visits dates reported} - Start date of Sunitinib + 1) / 30.44 					
	Note: Start date of Sunitinib will be the one reported:					
	- at time of Sunitinib initiation visit for patients enrolled at SU initiation (cf. CRF page 11 " Therapy started with Sunitinib in 1st line on ")					
	- at time of Axitinib initiation visit for patients enrolled at AXI initiation (cf. CRF page 26 "Therapy started with Sunitinib in 1st line on")					

- Best Response under Axitinib in 2nd line post Sunitinib

Number and percentages of patients by best response (CR, PR, SD or PD) will be presented.

- Objective Response Rate (ORR) under Axitinib in 2nd line post Sunitinib

ORR is defined as the percentage of patients with complete response (CR) or partial response (PR) according to RECIST from the start to the end of Axitinib treatment (cf. CRF page 29).

Patients who die, progress, or drop out for any reason prior to reaching a CR or PR will be counted as non-responders in the assessment of ORR.

All assessments following an assessment of PD will be excluded from the derivation of ORR.

- Clinical benefice Rate (CBR) under Axitinib in 2nd line post Sunitinib

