8.2.4 Analyses of Quality of Life Endpoints

Quality of life analyses will be provided in the FAS population on the SU-AXI subgroup. According to the questionnaire date, time windows will be derived according to the rule explain in section **Error! Reference source not found.** In case of missing or partial date, questionnaires will not be analyzed.

Quality of life will be analyzed using descriptive statistics at the treatment initiation, on the first 6 months and on AXI discontinuation overall and according to the best response observed under Axitinib treatment (CR, PR, SD, and PD):

- the FKSI-19 global score,
- the FKSI DRS-P subscore,
- the FKSI DRS-E subscore,
- the FKSI TSE subscore,
- the FKSI FWB subscore,
- the SF36 MH subscore,
- and the SF36 RE subscore.

Same analysis will be repeated on changes in scores/subscores from Baseline.

In order to explore possible variations in time and the possible differences according to the best response observed under Axitinib treatment, each changes in scores/subscores mentioned above will be analyzed using a mixed model for repeated measures (MMRM) according to the method described in section 8.1 of this document (Analysis of longitudinal data).

Estimated mean changes in scores/subscores from baseline will be provided and represented graphically with their 95% confidence interval:

- monthly (on the first 6 months),
- for each best response observed under Axitinib treatment (CR, PR, SD, and PD),
- in case of a statistically significant interaction between time and best response observed under Axitinib treatment, monthly estimated means will also be provided according to best response observed under Axitinib treatment (CR, PR, SD, and PD)

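### The overall monthly QoL mean changes are taken from a model with best-response terms, with no weighting, empty-cell rule or category for patients without a response

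*SAP*

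**What the plan says.** SAP 8.1.4 specifies one mixed model for repeated measures (MMRM) per QoL score, fitted "using the SAS MIXED procedure". Its categorical terms are "The time, the best response observed under Axitinib treatment, and the interaction between these 2 covariates as fixed effects". It also has "The Baseline value and baseline-x-time interaction as covariates".

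SAP 8.2.4 states what is taken from that model: "Estimated mean changes in scores/subscores from baseline will be provided and represented graphically with their 95% confidence interval". Three sets of means are listed:
- by month, "monthly (on the first 6 months", not split by response;
- by best response, with the four levels complete response (CR), partial response (PR), stable disease (SD) and progressive disease (PD);
- by month within response, only if the time-by-response interaction is significant.

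The best-response endpoint in SAP 6.1.2 has the same four levels: "Number and percentages of patients by best response (CR, PR, SD or PD) will be presented". The axitinib follow-up visit in the protocol's case report form (Annex 1, section 4.2) has a fifth option, not assessable (NA).

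SAP section 7 says the MMRM covers every patient with a baseline score and one or more later scores. It sets no condition on response. On collection, protocol 8.2 says: "The QoL questionnaire will be completed at baseline and then every month for patients receiving AXI". A further questionnaire is planned when axitinib stops.

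The SAP names no second model without response, no weighting for the estimated means, no rule for empty month-by-response cells and no level for patients without one of the four responses. Appendix A2.1, where further statistical detail would go, is marked not applicable.

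**The concern.** An overall monthly mean should describe the patients who were treated. When the model also contains response and time-by-response, that mean has to be built from four response-specific means, and the result depends on the weights. The SAP gives none, so the programmer is likely to get the software default.

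Three consequences would follow:
- The overall curve would describe an equal mix of the four response classes. A few CR patients, or a few PD patients still returning forms late on, would carry a quarter of the estimate each.
- If any response class has no form in a month, that month's overall mean could not be estimated.
- Patients without a CR, PR, SD or PD classification would leave the analysis, although SAP section 7 includes them.

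At stake is how well the model-based curves serve the secondary objective of measuring QoL on axitinib.

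**Working it through.** The documents give no figure for this model (no SD, response mix or QoL sample size), so there is no planned figure to reproduce. The structure comes from the SAP. All counts, shares and mean changes below are assumptions.

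**Weights.** Let m(t,r) be the adjusted mean change in month t for response r. The default MIXED mean for month t is

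[m(t,CR) + m(t,PR) + m(t,SD) + m(t,PD)] / 4.

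A patient-weighted mean is Σ n(r)·m(t,r) / N.

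**Precision.** Assume independent observations with common SD σ, and ignore baseline adjustment and within-patient correlation. Then
- equal-weight SE = (σ/4)·√(Σ 1/n(r));
- patient-weighted SE = σ/√N;
- ratio = √N·√(Σ 1/n(r)) / 4.

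| Assumed counts in a month (CR, PR, SD, PD) | N | SE ratio |
|---|---|---|
| 5, 60, 110, 60 | 235 | 1.89 |
| 3, 50, 100, 40 | 193 | 2.16 |
| 2, 40, 80, 10 | 132 | 2.29 |
| 1, 30, 60, 3 | 94 | 2.85 |
| 3, 60, 147, 90 | 300 | 2.63 |

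For the last row: √(1/3 + 1/60 + 1/147 + 1/90)/4 = 0.1516, and 1/√300 = 0.0577. The ratio is 2.63, an effective sample of about 43 out of 300. With 6 CR and 144 SD instead (CR 2%), the ratio is 1.94.

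**Shift in the mean.** Assume true changes of +1, 0, −2 and −6 for CR, PR, SD and PD. The equal-weight mean is (1 + 0 − 2 − 6)/4 = −1.75 in every case.
- Counts 3, 60, 147, 90: patient-weighted mean = (3 + 0 − 294 − 540)/300 = −2.77. Equal weighting is 1.02 points higher.
- Counts 1, 30, 60, 3: patient-weighted mean = (1 + 0 − 120 − 18)/94 = −1.46. Equal weighting is 0.29 points lower.

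The direction therefore depends on the mix. The FKSI-19 total runs from 0 to 76.

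**Estimability.** The interaction gives each month-by-response cell its own parameter. With no observation in a cell, that parameter is not identified, and neither is an average that puts weight on it. The repeated-measures covariance cannot supply it. A rank check on the 6-month by 4-response design gave:

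| Situation | Equal weights | Overall observed margins (OM) | Margins within month (OM with BYLEVEL) |
|---|---|---|---|
| All cells filled | 6 of 6 months | 6 of 6 | 6 of 6 |
| PD empty in months 5 and 6 | months 5 and 6 lost | months 5 and 6 lost | 6 of 6 |
| CR empty in month 1 | month 1 lost | month 1 lost | 6 of 6 |

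Adding baseline and baseline-by-time, with PD empty in months 5 and 6, left the equal-weight result unchanged. The mean over time for the response with the empty cell is lost as well. If a response never occurs at all, its level disappears and the months are estimable with weight 1/3 each.

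**Chance of an empty cell in a given month.** P = (1 − share × fraction returning a form)^N. The planned SU-AXI group is 350. Protocol 8.2 lets some patients be exempted from QoL locally, so 200 is shown as an assumed lower figure.
- CR share 1 to 3%, 60% returning forms: 12% down to 0.2% at N = 350; 30% down to 3% at N = 200.
- PD share 30%, 1 to 5% returning forms: 35% down to 0.5% at N = 350; 55% down to 5% at N = 200.

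**Excluded patients.** MIXED omits records with a missing class variable. If 5, 10 or 20% of 350 had no assessable response, about 18, 35 or 70 patients would be lost.

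**The case against.** The strongest reply is that the QoL objective is served elsewhere. Protocol 8.7.2 plans FKSI-19 means with SDs, 95% confidence intervals and medians at each assessment, for observed values and changes from baseline, and similar statistics for the two SF-36 domains. SAP 8.2.4 repeats descriptive summaries overall and by best response. These are patient-weighted; the overall ones need no response class and cannot become non-estimable. This stands, and it confines the defect to the model-based means and their graphs.

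Four stronger readings are tempting but unsupported:
- *The SAP prescribes equal weighting and deletion of unassessed patients.* It does neither. Both are software defaults, and the table shells are in separate documents. The fault is silence where a choice is needed, plus a conflict with section 7.
- *PD cells will be empty by months 4 to 6.* Scans about every two months and QoL collection tied to axitinib make thin late cells plausible, but nothing says when PD patients stop returning forms. The probabilities above run from 0.2% to 55%. A large PD share and an empty PD cell also cannot describe the same month.
- *The excluded patients are mainly early failures, so the curve is flattering.* The documents do not say who they would be.
- *Showing monthly by-response means only after a significant interaction hides results.* Descriptive by-response changes are planned unconditionally, so this is a matter of preference. So is pooling CR with PR.

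**Conclusion.** The point holds in a limited form. As written, the overall monthly mean changes have no stated weighting. Under the MIXED default they average CR, PR, SD and PD equally, so they do not describe the treated patients and lose precision when CR or late PD cells are small. The loss of a month's mean with an empty cell is algebra; only its likelihood is assumed. The exclusion of patients without a response class follows unless they get their own level, and SAP section 7 and SAP 8.1.4/8.2.4 need reconciling on this.

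Under the assumed counts the standard error rises by a factor of about 1.9 to 2.9, and the mean may move either way. These figures illustrate and do not predict. QoL is secondary, the model is exploratory, and PFS and TTF are untouched. This should be corrected before analysis, but it does not threaten the study's main results.

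**What to change.** Add to SAP 8.1.4 and 8.2.4 a companion MMRM per score with time, baseline and baseline-by-time only, fitted in the full section 7 population. Take the overall monthly mean changes and their graph from it. Each month with data is then estimable, and patients without a response class stay in. Keep the response model for the by-response question.

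If any overall mean is still taken from the response model, weight it by the observed response mix within each month (OM with BYLEVEL) and give NA or no response its own level. Overall observed margins alone are not enough, because months with an empty cell stay non-estimable.

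The cost is SAP wording and one extra model for each of the seven scores. No new data are needed.
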